### **8.4 Protocol Deviations**

The list of protocol deviations will be compiled prior to database lock. All deviations will be reviewed and decisions for handling each of the deviations will be made prior to the start of data analysis.

### **8.5 Demographics, Variables and Covariates**

Age will be collected as a continuous measure, with all participants being  $\geq 18$  years of age. Age strata will be defined as stratum 1: 18-25 years old, stratum 2: 26-41 years old, stratum 3: 42-57 years old, stratum 4: 58-67 years old, stratum 5: 68-76 years old, stratum 6: 77-94 years old, 95+ years old. Age will be considered for secondary analysis.

Sex will be collected as a categorical equal to 0=male and 1=female. Sex will be considered for secondary analysis.

Race/Ethnicity has been requested by the division as a covariate and will be considered for secondary analysis.

### **8.6 Handling of Missing Values**

All missing data will be quantified in the final report and possible biases for any missing data will be reported.

### **8.7 Statistical Analysis of Study Endpoints**

Statistical analyses will be conducted in SAS® software, Version 9.4 or higher of the SAS System for Windows (Copyright © 2013 SAS Institute Inc.) or other appropriate statistical software.

All continuous variables will be summarized using the following descriptive statistics: n (non-missing sample size), mean, standard deviation, median, maximum and minimum. The frequency and percentages (based on the non-missing sample size) of observed levels will be reported for all categorical measures. In general, all data will be listed, sorted by site, treatment and subject, and when appropriate by visit number within subject. All summary tables will be structured with a column for each treatment in the order (Control, Experimental) and will be annotated with the total population size relevant to that table/treatment, including any missing observations. 95% confidence intervals will be calculated for all means.

### **8.8.1 Primary Endpoint**

Incidence of wound edge apposition without dehiscence or need of re-approximation following wound closure.

Counts will be collected of participants not requiring wound re-approximation for both Opticlose and Dermabond. A Chi-Square test will be used to compare the observed frequencies of adverse events between the two products. The test statistic is calculated by comparing the observed frequency to the expected frequency under the null hypothesis. The p-value will be obtained to determine the statistical significance of the observed difference.

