## **6. STUDY PROCEDURES AND ASSESSMENTS**

### **6.1 Participant Screening and Informed Consent**

The pre-visit may take up to 30 minutes. Study staff will screen potential participants and obtain informed consent during this time as described in Section 5.

Participants will be randomized depending on the predicted incision size. If the incision site is large enough to require the use of the mesh and glue combination, participants will be randomized into the OptiClose Secure group or the Dermabond Prineo group. If the incision site is determined to be small enough that it does not require a mesh, participants will be randomized into the OptiClose Rapid group or the Dermabond Advanced group.

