### **8.2 Randomization**

The order of products tested first or second will be randomly assigned according to a randomization table developed by the biostatistics team. We will conduct a two-arm, prospective, unblinded, randomized prospective control trial by which participants will be randomly assigned to either receive treatment A: the Dermabond wound closure adhesive or the treatment B: OptiClose wound closure adhesive in participants undergoing the closure of any subcutaneous tissue following surgical site incisions. After assignment to treatment arm per incisional length requirements, participants will be randomized using

simple randomization, with 15 participants designated to receive Opticlose and 15 to receive Dermabond. Participants will be patients undergoing a skin closure of a full thickness surgical incision. For the products tested in this study, a total of 60 participants will be required to complete the study, 30 in each incisional length group. If a participant is unable to complete the study, the participant will be replaced such that the new participant will be assigned to the randomization cohort of the replaced participant.

Enrollment will continue until the study from the evaluable number of participants (60) is completed.

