#### **Incidence of Surgical Site Infections**

The incidence of surgical site infections (SSIs) will be recorded for each subject (as occurring within 30 days of treatment). Descriptive statistics will include the total number of infections. Comparative analysis between treatment groups will be conducted using Chi-Square tests or Fisher's exact test if the expected frequencies are low.

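### The primary chi-square compares the two brands without regard to the incision-length groups used for randomisation, and has no exact fallback for sparse counts

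*Combined protocol and SAP*

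**What the plan says.** **Randomisation.** Section 6.1 assigns by predicted incision size. For incisions needing mesh, "participants will be randomized into the OptiClose Secure group or the Dermabond Prineo group"; for the smaller ones, "participants will be randomized into the OptiClose Rapid group or the Dermabond Advanced group". Section 8.2 repeats the order of steps ("After assignment to treatment arm per incisional length requirements") and gives the numbers: "with 15 participants designated to receive Opticlose and 15 to receive Dermabond", with "a total of 60 participants will be required to complete the study, 30 in each incisional length group". That makes two strata of 15 v 15, with a different product pair in each.

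**Primary analysis.** Section 8.8.1 first says "Counts will be collected of participants not requiring wound re-approximation for both Opticlose and Dermabond". The test then follows: "A Chi-Square test will be used to compare the observed frequencies of adverse events between the two products". It mentions no length group, continuity correction, exact alternative or confidence interval.

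**Elsewhere.** For SSI, section 8.8.2 allows a chi-square or Fisher's "exact test if the expected frequencies are low". The ICDRG grade proportions in the same section get a chi-square with no such fallback. Section 8.7 lays out summary tables with one column per treatment and promises 95% confidence intervals for means only, so no interval is planned for the primary proportion.

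**The concern.** There are two gaps in the same short section.

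1. **Which comparison is made.** The design contains two randomised comparisons of different products. The analysis names a single contrast between brands and does not say whether the length groups are combined, stratified or tested separately. If one product pair differs and the other does not, nothing in section 8.8.1 commits the sponsor to showing that.
2. **Sparse counts.** With 30 per brand, or 15 per product in a length group, an uncommon failure leaves very small cells. The plan recognises this for SSI and supplies a remedy, but not for the primary endpoint.

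At stake is a primary p-value that may not exist, or whose side of 0.05 depends on an unstated choice between tests. Section 8.1 says superiority results are being reported because the non-inferiority results were indeterminate, so this p-value would carry the conclusion. An open choice between tests also leaves room for one made after seeing the data.

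**Working it through.** **Inputs from the documents.** 15 v 15 in each of two length groups, so 30 v 30 by brand and 60 in all (section 8.2).

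**Inputs that are assumptions.** The documents give no dehiscence or re-approximation rate, so I use 1% to 10%, with the thresholds shown. No alpha is stated for the primary test, so I use two-sided 0.05. Chi-square means the uncorrected Pearson statistic, which section 8.8.1 does not specify.

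**The plan's own figure.** None exists for the primary endpoint. The only design figure is the detectable difference in dry time in section 8.1, 0.02226. Its stated inputs (SD 0.01, 15 v 15, one-sided 0.025, 90% power) give 0.01226. That is a separate matter and plays no part below.

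**Step 1: expected failures per arm = n × rate.**

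| Assumed rate | 30 per brand | 15 per product in a length group |
|---|---|---|
| 1% | 0.3 | 0.15 |
| 3% | 0.9 | 0.45 |
| 5% | 1.5 | 0.75 |
| 10% | 3.0 | 1.5 |

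An expected count of 5 needs 5/30 = 16.7%, or 5/15 = 33.3% within one length group.

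**Step 2: chance of no failures = (1 − rate)^n.** With no failures the chi-square is 0/0.
- Over 60 participants: 0.99^60 = 0.547; 0.97^60 = 0.161; 0.95^60 = 0.046.
- In one length group of 30: 0.740, 0.401 and 0.215.

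**Step 3: borderline tables.**
- 4/30 v 0/30. Pearson: 60 × (4×30 − 0×26)² / (30×30×4×56) = 864,000/201,600 = 4.286, p = 0.038. Fisher: 2 × C(30,4)/C(60,4) = 2 × 27,405/487,635 = 0.112.
- 4/15 v 0/15. Pearson: 30 × (4×15)² / (15×15×4×26) = 108,000/23,400 = 4.615, p = 0.032. Fisher: 2 × 1,365/27,405 = 0.0996.
- 5/30 v 0/30: 0.020 v 0.052. 6/30 v 1/30: 0.044 v 0.103.
- Against zero failures with 30 v 30, Pearson first falls below 0.05 at 4 failures and Fisher at 6.

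**Step 4: type I error, enumerating every 30 v 30 table.**

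| Assumed rate in both arms | Pearson | Fisher |
|---|---|---|
| 3% | 1.0% | under 0.1% |
| 5% | 2.8% | 0.15% |
| 10% | 5.4% | 0.9% |

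The largest Pearson value at any common rate is about 5.5%, both for 30 v 30 and for 15 v 15.

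**Step 5: effect of stratifying and of exact testing.** Take assumed comparator failure rates of 5% (mesh) and 1.7% (glue only), with 15 v 15 in each. An odds ratio of 6 turns these into 24% (odds 0.0526 × 6 = 0.316; 0.316/1.316) and 9.4% (odds 0.0173 × 6 = 0.104; 0.104/1.104).

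| Test | Rejection, no difference | Rejection, odds ratio 6 |
|---|---|---|
| Pearson, groups combined | 1.2% | 44.0% |
| Cochran-Mantel-Haenszel (CMH) | 1.2% | 44.1% |
| Fisher, groups combined | under 0.1% | 18.8% |
| Exact stratified | 0.1% | 25.6% |

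Stratifying matters more only when the groups differ sharply. At assumed failure rates of 40% and 5% with no product difference, combined Pearson rejects in about 3% of trials and CMH in just under 5%.

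**The case against.** The other side has a good deal on its side.

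- **The chi-square is not liberal here.** A reader might infer from the small expected counts that false positives are inflated. Step 4 shows otherwise: at 3% to 5% failure the test is conservative, and its worst case is about 5.5%. With no true difference, Pearson and Fisher part company in only about 1% of trials at 3% failure and 2.7% at 5%. This stands, and the point does not rest on inflation. With a real difference the choice weighs more: in the odds ratio 6 scenario, 44.0 − 18.8 = 25.2 percentage points separate the two tests when the groups are combined.
- **Combining the groups does not confound the brand comparison.** Allocation is planned as 15:15 in each group, no passage links incision length to dehiscence, and Step 5 shows almost no change in rejection at low rates. This stands too. The case for stratifying is mainly about which comparison is estimated and shown.
- **The test may not be meant to combine the groups.** Section 8.8.1 says neither pooled nor Pearson, and the sample size is set per length group, so separate tests are a possible reading. Combining is the natural reading of counts taken by brand, but it is not stated. The defect is that the plan leaves it open.
- **No failures means no conclusion is lost.** Fisher's p would be 1. True, but the plan does not say what would then be reported.
- **Exact tests are costly with 60 participants.** Step 5 confirms this, and the fix has to say so.

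**Conclusion.** The point holds as a gap in specification with a modest numerical consequence. Section 8.8.1 takes no account of the groups within which participants are randomised, and it omits the low-count rule the same plan gives to SSI.

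The sparse-cell finding needs only a failure rate below 16.7% over both groups, or below 33.3% within one. The zero-failure probabilities depend on the assumed rate and drop quickly: about 0.2% over 60 participants at 10%. The power figures belong to one assumed scenario.

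Two stronger readings are not supported. A reader might infer that about one failure per arm is expected. That needs a rate near 3.3%, which appears nowhere in the documents. A reader might also call the primary p-value unreliable. Its overall error rate is acceptable; the weakness is confined to borderline tables and to the case of no failures.

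**What to change.** In section 8.8.1:

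1. State that the apposition endpoint (not adverse events, as the test sentence now reads) is compared with a CMH test stratified by incision-length group.
2. Report failures and denominators for each product pair, plus a stratified Miettinen-Nurminen risk difference with 95% CI. A single common estimate would still mix two product pairs, so the per-pair counts are essential.
3. Extend the SSI low-count rule to this endpoint and to the ICDRG grade proportions, using an exact stratified version. Say what low means (by convention, an expected count below 5) and whether it is judged overall or within a length group. With equal arms, below 5 means fewer than 10 failures among those counted, so expect the exact version to be the one used.
4. Say what is reported if nobody fails: counts and the interval, with no test.
5. If outcome data have already been seen, as section 8.1 suggests, label this analysis post hoc.

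**Cost.** Wording and standard software; no new data, because length group is fixed before randomisation. The real price is power: in the scenario above the exact stratified test rejects in 25.6% of trials against 44.0% for the chi-square. It does better than Fisher on the combined groups (18.8%). The plan should therefore state that the risk difference and its interval, rather than the p-value, carry the interpretation.

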**Endpoints:**

*Primary Endpoint:* Incidence of wound edge apposition without dehiscence or need of re-approximation following wound closure.

*Secondary Endpoint:* Secondary endpoints include:

- Surgical Site Infections (SSIs) (criteria defined by the CDC), if applicable
- Inflammatory reactions as calculated by the International Contact Dermatitis Research Group (ICDRG) grading system (see appendix), if applicable.
- Cosmesis as assessed by the Modified Hollander score (see appendix).
- Dry time as objectively measured by an observer/end user.
- Number of applicator tubes/mesh used.

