**1.2. Schedule of Activities (SOA)**

	Pre-Op	Post Op	Post Op Follow Up 1	Post Op Follow Up 2
Informed Consent/Subject Enrollment	x			
Product Application to surgical site		x		
Dry time recording (with stopwatch)		x		
Number of applicator tubes used		x		
Circulating Nurse notes assessment for adverse events related to allergic reactions. IF applicable, preforms the International Contact Dermatitis Research Group (ICDRG) grading system		x	x	x
Incidence of Surgical Site Infection (SSIs). If applicable performs the CDC criteria for SSI.		x	x	x

Incisional Site Wound Dehiscence Check (inspection of wound edge approximation).			X	X
Incisional Site Cosmesis Score Check using Modified Hollander Scale			X	X
Incisional Site Photos*		X	X	X
Subject Dismissal				X
*Only applies to participants who have consented to incisional site photos.				

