## **2.3. Risk/Benefit Profile**

### **2.3.1 Potential Study Risks**

This study entails minimal risk to study participants for the Opticlose approximation, which includes commercially available products that can be used in the clinical settings and are designated for use as per the study design. There is a possibility of minor skin irritation and redness, sensation of heat and discomfort, or wound dehiscence. However, the magnitude of this should be no greater than what occurs through normal use of the currently marketed topical skin adhesives. The topical adhesives will only be applied to area(s) of surgical incision which should further minimize risk. Each product used in this study would have been tested for its biocompatibility for dermal irritation and within acceptable parameters of the International Organization for Standardization (ISO) 10993-10 requirements. A small but potential risk of allergic skin reaction may occur as a known risk with use of acylate based wound closure devices.

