### **6.3 Follow-up post-operative visit (Visit 2 & 3)**

In the second and third post-operative visits, the incisional wounds will be assessed for possible dehiscence and the results will be recorded. Moreover, an incisional site cosmetic score will be obtained using the Modified Hollander score for linear scars and will be used to further assess and categorize the current wound state. As with the first visit, the research staff will also assess any potential adverse event that may have resulted from the use of the topical adhesives. Additionally, any incidence of surgical site infections will be noted. Following the assessments during the third visit, the participants will be dismissed from the study. The CDC SSI and ICDRG grading systems will be used if either of the two events are deemed applicable by the study staff.

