## **8 STATISTICAL CONSIDERATIONS**

### **8.1. Sample Size Determination**

The purpose of this study is to show non-inferiority between the two products. We are reporting superiority results, as the noninferiority results were indeterminate. A sample size of 30 per incisional length group was estimated based on the secondary outcome of difference in mean “Dry Time” using estimated means (no standard deviations) from the vendor for both OptiClose and Competitor product, and estimation of effect size. The comparison will be made using a one-sided, two-sample unequal-variance t-test, with a Type I error rate ( $\alpha$ ) of 0.025. The standard deviation for Group 1 is assumed to be 0.01 and the standard deviation for Group 2 is assumed to be 0.01. With sample sizes of 15 in OptiClose Product and 15 in Dermabond, and with 90% power, the corresponding detectable difference in means is 0.02226. Provided exact standard deviations, an exact difference can be adjusted accordingly. The detectable difference was computed using PASS 2024, version 24.0.2.

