#### **8.8.4 Adverse Device Events**

All adverse device events will be included in the analyses and report documents, including but not limited to skin irritation, redness, and itching.

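### The count and test sentences of section 8.8.1 do not match the primary endpoint: one counts only re-approximation, the other compares adverse events, and neither names dehiscence

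*Combined protocol and SAP*

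**What the plan says.** The synopsis defines the primary endpoint as "Incidence of wound edge apposition without dehiscence or need of re-approximation following wound closure", and section 8.8.1 opens with the same definition. Two operational sentences follow:

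- The count: "Counts will be collected of participants not requiring wound re-approximation for both Opticlose and Dermabond".
- The test: "A Chi-Square test will be used to compare the observed frequencies of adverse events between the two products".

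On data collection, the Schedule of Activities (section 1.2) lists this item at both follow-up visits: "Incisional Site Wound Dehiscence Check (inspection of wound edge approximation". Section 6.3 says that at visits 2 and 3 "the incisional wounds will be assessed for possible dehiscence and the results will be recorded". Neither place names a separate re-approximation item.

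On adverse events, section 8.8.4 says: "All adverse device events will be included in the analyses and report documents, including but not limited to skin irritation, redness, and itching". The risk section (2.3.1) does mention dehiscence: "There is a possibility of minor skin irritation and redness, sensation of heat and discomfort, or wound dehiscence".

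Section 8.8.3 plans no supplemental analyses, so no later section supplies an analysis of the endpoint as defined.

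**The concern.** A primary analysis should test the primary endpoint. Section 8.8.1 carries three variables: the composite in its opening line, a re-approximation count, and adverse-event frequencies. No rule combines dehiscence and re-approximation into one success or failure per participant.

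Two things are at stake. An analyst who follows the text produces a primary p-value that does not answer the primary question. An analyst who does not follow it has to choose a variable, and the plan does not say which one. With 15 participants per product in each incision-length group, a difference of a few wounds between definitions can decide the result.

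**Working it through.** The plan attaches no figure to the primary endpoint. Its only power calculation was "estimated based on the secondary outcome of difference in mean" dry time, so there is nothing to reproduce here. The check is a comparison of texts, followed by an illustration of size.

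**Step 1. Classify typical participants under each sentence.**

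| Participant | Endpoint (synopsis; first line of 8.8.1) | Count sentence | Test sentence |
|---|---|---|---|
| Wound intact, no reaction | Success | Success | No event |
| Wound intact, itching or redness | Success | Success | Event |
| Dehiscence, judged not to need re-approximation | Failure | Success | Event only if recorded as an adverse event |
| Re-approximation needed | Failure | Failure | Event only if recorded as an adverse event |

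The count sentence departs from the endpoint in row 3. The test sentence departs in row 2, and may depart in rows 3 and 4 depending on how events are recorded. The two sentences also disagree with each other in row 2, and can do so in rows 3 and 4. Correcting the noun in the test sentence alone would leave row 3 unresolved.

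**Step 2. Effect of one row-3 wound on a product's success rate.** The change is 1/n.

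- Section 8.2 assigns 15 participants to each product in each incision-length group: 1/15 = 6.7 percentage points.
- If the two groups are pooled, n = 15 + 15 = 30 per product: 1/30 = 3.3 points. Section 8.8.1 does not say whether they are pooled.

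**Step 3. Effect on the test.** Section 8.8.1 states no alpha, so two-sided 0.05 is assumed. For 0 failures against k, with n per product and pooled failure proportion p = k/(2n), the Pearson statistic is (k/n)² / [p(1 − p)(2/n)].

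- n = 15, k = 3: p = 0.10, statistic = 0.04/0.012 = 3.33, p-value 0.068.
- n = 15, k = 4: p = 0.133, statistic = 0.0711/0.0154 = 4.62, p-value 0.032.
- n = 30, k = 3: p-value 0.076.
- n = 30, k = 4: p-value 0.038.

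The expected number of failures per product is only k/2, at most 2 here, so the chi-square approximation is poor. Fisher's exact test gives 0.100 (k = 4) and 0.042 (k = 5) at n = 15, and 0.052 (k = 5) and 0.024 (k = 6) at n = 30. Under either test, the classification of a single wound can move the result across 0.05. The failure counts are hypothetical.

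**The case against.** The strongest reply is that this is a drafting slip. The paragraph on number of applicator tubes in section 8.8.2 uses almost the same test sentence with the tubes in the variable's place, so the wrong noun was probably left in a template. The section is also titled for the primary endpoint and opens with the full definition, dehiscence included. This is plausible and bears on intent. It does not repair the count sentence, which departs from the endpoint separately, and nothing elsewhere reconciles the three.

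A second reply is that dehiscence may enter as an adverse event, since section 2.3.1 lists it as a risk and the list in section 8.8.4 is open. That is possible, but it would then be pooled with skin reactions, which is still not the endpoint.

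A reader might also infer more than the documents support:

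- **That the counted variable is not collected.** Section 8.8.1 says the counts will be collected, and the case report forms are not in the documents. One can say only that the schedule and section 6.3 name no separate item.
- **That every dehiscence left without re-closure is a success under section 8.8.1.** The sentence turns on whether re-approximation was required, not on whether it was done. The wound is a success only if judged not to need it, and the documents do not define need.
- **That success will be overstated by a known amount.** The documents give no rate of dehiscence or of its management, and overstatement arises only if the count sentence governs.

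**Conclusion.** The point stands as a mismatch between the endpoint and the two sentences that put it into operation, and it should be corrected because it sits in the primary analysis. If the test sentence governs, the p-value is about adverse events. If the count sentence governs, a dehiscence judged not to need re-approximation is misclassified as a success.

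The text comparison needs no assumption. The sizes do: 6.7 points per wound assumes analysis within an incision-length group, 3.3 points assumes pooling, and the p-values assume a two-sided 0.05 level. How many wounds would be affected, and which product would gain, cannot be determined from the documents.

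**What to change.** Rewrite section 8.8.1 around one binary variable per participant. Success is no dehiscence recorded at follow-up 1 or follow-up 2, and no need of re-approximation from closure through follow-up 2. Anything else is a failure. Keep the endpoint's term need and state how it is determined; substituting re-approximation performed would create a new mismatch. Name this variable in both the count and the test sentence, and analyse adverse events only under section 8.8.4.

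Confirm that the case report form captures need of re-approximation, including between visits. If it does not, add the field at the two follow-up visits and a line in the schedule.

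Section 8.1 refers in the past tense to non-inferiority results as indeterminate, which suggests that results may already have been seen. If so, apply the definition to the dehiscence data already scheduled for recording, report what is and is not available on need of re-approximation, and disclose the change as post hoc.

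The cost is minor edits to the analysis plan and possibly the case report form. Reported success may be lower than under the count sentence.
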